2.8.1.1 Adverse events of special interest / grouping of AEs

AEs of special interest, such as risks defined in the development safety profiling plan (DSPP), or topics of interest regarding signal detection or routine analysis, are defined in the electronic case retrieval sheet (eCRS) that is stored in GPS.

The pre-defined issues of special interest for LIK066 including identified risks, potential risks, and special assessments are listed below:

- Bone fractures
- Cardiotoxicity
- Diarrhea
- Electrolyte disturbances
- Genital infections
- Hepatotoxicity
- Hypersensitivity
- Hypoglycemia
- Impaired renal function
- Increased LDL

- Intravascular volume depletion
- Ketoacidosis
- Malignancy
- Pancreatitis
- Urinary tract infections
- Venothrombotic and embolic events
- Lower limb amputation
- Pre-amputation events

Treatment-emergent AEs of special interest which occur during Epoch 3 will be summarized by risk category and preferred term, by treatment. The AEs of special interest will be summarized by risk category, preferred term, treatment, and subgroups of interest (baseline glycemc status, age group, and sex) as well.

In addition, exposure-adjusted incidence rates per 100 patient years regardless of study drug relationship, by treatment will be provided by risk category and preferred term. The 95% confidence interval for the overall exposure-adjusted incidence rates per 100 patients will also be presented for each risk category, along with relative risk and 95% confidence interval.

Additional analyses for the pre-defined risks of diarrhea, ketoacidosis and hypoglycemia will be performed as described below:

Diarrhea events of special interest

Number of days with diarrhea events will be calculated for all patients with at least one incidence of diarrhea and will be summarized descriptively by treatment.

- Number of days for one diarrhea incidence = AE end date – AE start date +1.
- Number of days with diarrhea events for a patient = sum of days on diarrhea over all incidences that occurred in Epoch 3.

The number and percentage of patients with diarrhea events during the double-blind treatment period (while patients on study medication) will also be summarized by treatment over time in the following time window: 0 - <2, 2 - <4, 4 - <8, and 8 - <12 weeks.

In addition, the number of days with diarrhea while on-treatment will be analyzed via a negative binomial regression model. The model will include the number of days with diarrhea as a response variable, treatment, baseline glycemc status as factors, and log(duration of exposure in days) as an offset variable.

Ketoacidosis events of special interest

All cases of ketoacidosis will be adjudicated by an independent committee. The frequencies and percentages of the adjudication confirmed ketoacidosis events will be provided by treatment.

The site-reported ketoacidosis events will also be summarized by treatment. In addition, the ketoacidosis events will be listed at individual patient level, with the site-reported event profile and symptoms and the adjudication outcome displayed as well.

Hypoglycemic events of special interest

There are two categories of clinically significant hypoglycemic events:

Table 2-3 **Criteria for hypoglycaemia events**

Category	Criteria
Severe hypoglycaemia	An event, requiring assistance of another person (third party assistance) to actively administer carbohydrate, glucagon, or other corrective actions, confirmed or not by a blood glucose measurement
Other clinically significant hypoglycaemia	Plasma glucose < 3.0 mmol/l (54 mg/dl) with or without typical symptoms of hypoglycaemia, and which is handled by the subject himself/herself.

Hypoglycemic events entered into the study Hypoglycemic event eCRF will be included in all of the AE summaries in Section 2.8.1. Hypoglycemia classification is included in the Appendix Table 5-1.

In addition, patients reporting at least one clinically significant hypoglycemic event, and the subgroup of patients reporting ≥ 2 such events, patients discontinued study medication or withdrew from the study due to clinically significant hypoglycemic events, patients reporting severe hypoglycemic events, and patients reporting other clinically significant hypoglycemic events will be summarized by numbers and percentages in each treatment group. The exposure-adjusted incidence rates, relative risks and the related 95% confidence intervals of LIK groups versus placebo for the overall, severe and other clinically significant hypoglycemic incidences will be calculated respectively, and presented along with other safety risks/events of interest.

The clinically significant hypoglycemic events will also be summarized by event profile as follows:

- Severity (Mild, Moderate, Severe)
- Meeting the definition of an SAE (Yes, No)
- Seriousness (Death, Requires or prolongs hospitalization, Life threatening, Congenital anomaly or birth defect, Significant disability, Other medically importance serious event)
- Discontinuation due to hypoglycemic events (Yes, No)
- Relationship to the study treatment (No, Investigational treatment, Other study treatment, Both and/or indistinguishable)
- Action taken with study treatment (Dose increased, Dose not changed, Dose reduced, Drug interrupted, Drug withdrawn, Unknown, Not applicable)
- Medication or therapy taken (Yes, No)
- Outcome (Not recovered/not resolved, Recovered/resolved, Recovered/Resolved with sequelae, Fatal, Unknown)
- Time of the day in 24-hour clock (>00:00–06:00, >06:00–12:00, >12:00–18:00, or >18:00–24:00)
- Time between last meal and event
- Time between last dose and event
- Precipitating factors (None, Missed/delayed meal, Strenuous exercise, Alcohol consumption, Other)

- Third party assistance received (Yes, No)
- Medical assistance received (Yes, No)

In addition, for pre-defined risk and selected AEs including hypotension, hypoglycemia, hyperkalemia, diarrhea, genital infections and UTIs, a by-stratification factor of BL glycemc status subgroup analysis will be provided.

A listing of AEs of special interest will be presented by treatment group and patient number.

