2.1.1 General definitions

Baseline (Week 0) for the randomized treatment period will be defined as the last measurement before or at the randomization visit.

The first day of administration of randomized study treatment (first dose) is defined as Day 1 for the study. If the date of first administration is missing, then randomization date will be used as Day 1.

All other study days will be labeled relative to Day 1. For event dates on or after Day 1, study day for a particular event date is calculated as [Date of event] – [Date of first dose] + 1. For the dates before Day 1, study day for an event date is calculated as [Date of event] – [Date of first dose]. Duration of an event will be calculated as [Event end date] – [Event start date] + 1. The descriptor "Day 0" will not be used.

The treatment groups presented are:

- LIK066 2.5 mg qd
- LIK066 10 mg qd
- LIK066 25 mg qd
- LIK066 50 mg qd
- Placebo
- Total (if applicable)

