For the legal requirements of ClinicalTrials.gov, two required tables on treatment emergent AEs which are not SAEs with an incidence greater than 2% and on treatment emergent SAEs and SAEs suspected to be related to study treatment will be provided by system organ class, preferred term, and 5 randomized treatment arms on the SAF for overall study duration.

If for a same patient, several consecutive AEs (irrespective of study treatment causality, seriousness and severity) occurred with the same SOC and PT:

- a single occurrence will be counted if there is ≤ 1 day gap between the end date of the preceding AE and the start date of the consecutive AE
- more than one occurrence will be counted if there is > 1 day gap between the end date of the preceding AE and the start date of the consecutive AE

For occurrence, the presence of at least one SAE/SAE suspected to be related to study treatment/non SAE has to be checked in a block e.g., among AE's in a ≤ 1 day gap block, if at least one SAE is occurring, then one occurrence is calculated for that SAE.

The number of deaths resulting from SAEs suspected to be related to study treatment and SAEs irrespective of study treatment relationship will be provided by SOC and PT.

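### The SAP's days-with-diarrhea variable adds up record lengths, so a calendar day covered by more than one diarrhea record is counted more than once

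*SAP*

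**What the plan says.** SAP 2.8.1.1, under the diarrhea events of special interest, builds the variable in two steps. The length of one event is "Number of days for one diarrhea incidence = AE end date – AE start date +1". The patient's total is the "sum of days on diarrhea over all incidences that occurred in Epoch 3". The general rule in SAP 2.1.1 is the same inclusive count: "Duration of an event will be calculated as [Event end date] – [Event start date] + 1". Neither section mentions overlapping events.

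The variable is used twice. It is summarized by treatment for patients with at least one event. In addition, "the number of days with diarrhea while on-treatment will be analyzed via a negative binomial regression model", with treatment and baseline glycemic status as factors and log exposure in days as the offset. The SAP's document history shows that the July 2018 amendment revisited this model to restrict it to on-treatment days.

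The SAP has one rule for merging records. In SAP 2.8.1, for several consecutive events with the same system organ class and preferred term, "a single occurrence will be counted if there is ≤ 1 day gap between the end date of the preceding AE and the start date" belonging to the next one. That rule is introduced by "For the legal requirements of ClinicalTrials.gov, two required tables on treatment emergent AEs" and concerns occurrence counts. It is not carried over to the diarrhea-days variable.

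**The concern.** The variable is named as a number of days, and a reader will take it as the number of calendar days on which the patient had diarrhea. A sum of record lengths equals that number only if no two records share a date. Where they do, the total overstates the patient's diarrhea burden, and in an extreme case it can exceed the days of exposure that form the model's offset.

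The SAP's own text leaves two routes to shared dates:

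- **Consecutive same-term records.** The ClinicalTrials.gov rule provides for these. A gap of at most one day includes the case where the second record starts on the end date of the first.
- **Partial dates.** The imputation rules in SAP 5.1.2 can give two separate episodes in the same month identical start and end dates.

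Diarrhea is one of the pre-defined issues of special interest, and tolerability is part of what the study is meant to contribute to Phase 3 dose selection. A days variable used in a between-arm model should therefore measure what its name says.

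**Working it through.** The plan states no figure for this variable, so there is nothing to reproduce. The check applies the SAP's formula to record pairs and compares it with the number of distinct calendar days. All dates are illustrative assumptions. The only input from the documents besides the formula is the 12-week treatment period, 12 × 7 = 84 days.

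**Formulas**

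- SAP total = sum over records of (end − start + 1).
- Distinct days = number of calendar days covered by at least one record.
- A day covered by m records enters the SAP total m times, so the excess is the sum of (m − 1) over all covered days.

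**Results**

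| Records (study days) | SAP total | Distinct days | Excess |
|---|---|---|---|
| 1–5 and 10–12 (gap) | 5 + 3 = 8 | 8 | 0 |
| 1–5 and 6–10 (next day) | 5 + 5 = 10 | 10 | 0 |
| 1–5 and 5–10 (one shared date) | 5 + 6 = 11 | 10 | 1 |
| 1–5, 5–8 and 8–10 (two shared dates) | 5 + 4 + 3 = 12 | 10 | 2 |
| 1–10 and 6–15 (partial overlap) | 10 + 10 = 20 | 15 | 5 |
| 1–20 and 5–8 (nested) | 20 + 4 = 24 | 20 | 4 |
| 1–84 twice (extreme case) | 84 + 84 = 168 | 84 | 84 |

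Records that follow one another without a common date are summed correctly. Each junction where one record starts on another's end date adds one day. True overlap adds every shared day.

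**Partial dates.** Take two separate episodes in May, with the day missing from all four dates, treatment started in an earlier month of the same year, and last visit and last dose after May. Under SAP 5.1.2 the missing start day becomes the later of 1 May and the day after treatment start, so 1 May. The missing end day becomes the earliest of 31 May, the last visit or last dose, and death, so 31 May. Both episodes then run 1–31 May. The SAP total is 31 + 31 = 62, against 31 distinct days. This applies only if imputed dates feed the variable, which the SAP does not say.

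**Effect on the model.** Suppose overlap multiplies mean days by (1 + a) in an active arm and by (1 + p) in placebo. With the same exposure offset, the rate ratio is multiplied by roughly (1 + a)/(1 + p). If a = p, the ratio is unchanged. If a > p it is inflated, and if a < p it is attenuated. The documents give neither a nor p.

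**The case against.** The best defence has four parts.

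1. **An incidence need not be a raw record.** The SAP sums over incidences, which could mean clinical episodes already collapsed from the database, and the target is called days with diarrhea. This is a fair reading of intent. But the formula works from the AE start and end dates, no collapsing step is given, and the one merging rule in the SAP is confined to other tables. A programmer following the text would sum the records.

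2. **Overlap may be rare.** Nothing says that a change in severity opens a new record. Protocol 7.1 has each event followed to resolution with changes in severity assessed at each visit, which fits a single record just as well. This stands, and it limits the size of the point: the frequency is unknown.

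3. **Full overlap through several preferred terms is not shown.** Because events of special interest "will be summarized by risk category and preferred term, by treatment", a reader might infer that the diarrhea category holds several terms and that two of them could cover the same days, doubling the count. The wording is common to all the risk categories, and the terms are defined in a retrieval sheet that is not part of the documents. The documents do not support relying on this route.

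4. **The ClinicalTrials.gov rule is about occurrences, not durations.** Leaving it out here is not in itself an inconsistency, and next-day records, which it also covers, cause no excess. This is correct. The rule shows only that consecutive same-term records are anticipated, some of which may share a date.

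**Conclusion.** The defect is real but small. Read as written, SAP 2.8.1.1 counts a calendar day once for every diarrhea record that covers it, and no other rule in the SAP prevents this. The excess is exactly the number of repeated days: none for records with no common date, one per shared junction date, and the whole overlap otherwise (5 days in the 20-against-15 example).

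Two stronger readings are tempting and should not be adopted. A reader might infer that any back-to-back records are double-counted; next-day records are not. A reader might also infer that the rule inflates the dose effect on diarrhea, because patients with more diarrhea have more records. More records do not by themselves mean a larger overlapping fraction, and a proportional overcount leaves the rate ratio where it was. Bias in the ratio is possible if the fraction differs by arm, but the documents do not show that it would.

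The conclusion assumes that records sharing dates occur at all, either as consecutive same-term records or through imputed dates. How often cannot be judged from the documents. Only the descriptive days summary and the negative binomial response are affected. The primary analysis and the counts of patients with diarrhea, including those by time window, are not.

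**What to change.** Define the variable in SAP 2.8.1.1 as the number of distinct calendar days covered by at least one record in the diarrhea category. Keep each existing window: days within Epoch 3 for the descriptive summary, and on-treatment days for the negative binomial model. There is no need to restrict the descriptive summary to on-treatment days.

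The cost is one SAP sentence and a short programming step, with no new data. The new definition gives the same answer as the current sum whenever no dates are shared, and it removes the double count whether or not imputed dates are used.

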2.8.2 Deaths

Any deaths up to and including Week 12 will be included in a separate table by treatment group summarizing fatal events.

Deaths will also be listed by treatment groups.

2.8.3 Laboratory data

Table 2-4 displays laboratory parameters analyzed for reporting.

Table 2-4 Laboratory data

Category	Parameter(s)
Hematology	RBC (total), WBC (total), platelet count (direct), hemoglobin, hematocrit, basophils (absolute, %), eosinophils (absolute, %), lymphocytes (absolute, %), monocytes (absolute, %), neutrophils (absolute, %)
Biochemistry	ALT, albumin, alkaline phosphatase (ALP), AST, bicarbonates, bilirubin (direct, total), blood urea nitrogen (BUN), calcium (total), chloride, creatinine, cystatin C, eGFR (MDRD, MDRD with the Japanese coefficient), magnesium, phosphates, potassium, protein (total), sodium, uric acid*, γ -GT, amylase, lipase
Urinalysis	pH, specific gravity, protein, glucose, ketones, nitrites, blood, leucocytes, urine albumin*, urine albumin to creatinine ratio (spot urine)*

*: By-visit summary statistics for the parameter is provided only as efficacy analysis.

Descriptive summary statistics including for the change from BL to each study visit up to and including Week 12 visit will be presented by treatment group for each laboratory parameter, as well as for the maximum change from BL. In addition, shift tables will be provided for all parameters with available ranges to compare a subject's BL laboratory evaluation relative to the most extreme post-BL value. For the shift tables, normal ranges as well as specifically defined clinically notable/abnormality limits, if available – will be used.

A listing of all patients with notable laboratory values will be provided.

Clinically notable laboratory abnormalities for selected tests based on a percent change from baseline are shown in Table 2-5.

Table 2-5 Clinically notable laboratory abnormalities for selected tests

Parameter	Criteria (based on a percent change from baseline or change from baseline)
Hematology	
RBC (total)	>50% increase, >20% decrease
WBC (total)	>50% increase, >50% decrease
Platelet count	>75% increase, >50% decrease
Hemoglobin	>50% increase, >20% decrease
Hematocrit	>50% increase, >20% decrease
Clinical chemistry	
ALT	>150% increase
AST	>150% increase
BUN	≥50% increase
Creatinine	≥50% increase
Total bilirubin	>100% increase
ALP	>100% increase
Sodium	>5% increase, >150 mmol/L, <130 mmol/L
Potassium	absolute values < 3.0 mmol/L, > 5.9 mmol/L
Chloride	>10% increase, >10% decrease
Calcium	>10% increase, >10% decrease, hyper > 2.6 mmol/L
Uric acid	>50% increase
Plasma glucose	>50% increase
Plasma glucose	< 3.0 mmol/L (54 mg/dL)

2.8.4 Other safety data

2.8.4.1 ECG and cardiac imaging data

The following quantitative variables will be summarized:

- QT_cF duration (msec)
- Heart rate (beats/min)
- PR duration (msec)
- RR duration (msec)
- QRS duration (msec)

Changes from baseline for ECG variables will be provided; for QT_cF and heart rate, inferential statistics will be generated as well.

The number and percentage of subjects with the following criterion will be presented.

- QT_cF > 500 msec
- QT_cF > 480 msec
- QT_cF > 450 msec

- QT_cF increases from baseline ≥ 30 msec
 - QT_cF increases from baseline ≥ 60 msec
 - PR > 200 and ≤ 220 msec
 - PR > 220 msec
 - PR increases from baseline $> 25\%$ and to a value > 200 msec
 - QRS > 110 and ≤ 120 msec
 - QRS > 120 msec
 - QRS changes from baseline $> 25\%$ and to a value > 110 msec
 - Heart rate > 100 beats/min
- Heart rate < 50 beats/min

In addition, shift tables comparing baseline ECG results (normal, abnormal, not available, total) with the maximum on-study result (normal, abnormal, not available, total) will be provided for each variable. The cut-off values are :

- QT_cF: 450 msec for male, or 460 for female
- QRS: 120 msec
- PR: 200 msec
- HR: 100 beats/min

A listing of ECG parameters together with newly occurring or worsening abnormalities will be provided.

2.8.4.2 Vital signs

For vital sign data collected during Epoch 3, descriptive statistics will be provided for absolute values and change from baseline at each assessment time point by treatment group as appropriate.

The number and percentage of patients with newly occurring or worsening notable values, including notable change from baseline will be summarized by vital sign parameter at each assessment time point by treatment group. Notable absolute values and notable changes from baseline for each vital sign parameter are defined in [Table 2-6](#).

Table 2-6 Vital signs notable range deviations

Vital signs		Notable abnormalities
Pulse (beats/min)		either ≥ 120 + increase $\geq 25^*$ or > 130 either ≤ 50 + decrease $\geq 30^*$ or < 40
BP (mmHg)	systolic	either ≥ 180 + increase $\geq 30^*$ or > 200 either ≤ 90 + decrease $\geq 30^*$ or < 75
	diastolic	either ≥ 105 + increase $\geq 20^*$ or > 115 either ≤ 50 + decrease $\geq 20^*$ or < 40

* Refers to post-BL value as compared to BL value.

A listing of all patients with notable vital sign values and changes will be provided.

2.8.5 Liver events

Liver events and laboratory trigger definitions and follow-up requirements are defined in Appendix 2 of the protocol.

The laboratory parameters for liver function will be shown in the laboratory standard tables as discussed in Section 2.8.3. In addition, summary tables will be provided on the number and percentage of subjects who meet the liver toxicity criteria post baseline by Week 12 displayed in Table 2-7.

Listings of patients with clinically notable LFT values will be provided.

Table 2-7 Criteria for evaluating liver toxicity

Parameter	Criterion
ALT or AST	ALT or AST > 3xULN ALT or AST > 5xULN ALT or AST > 8xULN ALT or AST > 10xULN
Hy's category	ALT or AST >3x ULN and TBL >1.5x ULN ALT or AST > 3xULN & TBL > 2xULN ALT or AST > 5xULN & TBL > 2xULN ALT or AST > 8xULN & TBL > 2xULN ALT or AST > 10xULN & TBL > 2xULN ALT or AST > 3xULN & TBL > 2xULN & ALP ≤ 2xULN
TBL&ALP	TBL >1.5x ULN and ALP >2x ULN TBL >2x ULN and ALP >2x ULN
Isolated TBL	TBL >1.5x ULN & ALT and AST ≤3x ULN and ALP ≤2x ULN TBL >2x ULN & ALT and AST ≤3x ULN and ALP ≤2x ULN TBL >3x ULN & ALT and AST ≤3x ULN and ALP ≤2x ULN
Isolated ALP	ALP >1.5x ULN & ALT and AST ≤3x ULN and TBL ≤1.5x ULN ALP >2x ULN & ALT and AST ≤3x ULN and TBL ≤1.5x ULN ALP >3x ULN & ALT and AST ≤3x ULN and TBL ≤1.5x ULN ALP >5x ULN & ALT and AST ≤3x ULN and TBL ≤1.5x ULN

ALP: alkaline phosphatase; ALT: alanine aminotransferase; AST: aspartate aminotransferase; TBL: total bilirubin; ULN: upper limit of normal.

2.8.6 Renal events

The overall frequency of events and percentage of patients with renal events during the treatment period will be provided for the Week 12 analysis. Furthermore, the frequency and percentage of patients with renal events during Epoch 3 will be provided by treatment and the first identified criterion. The frequency of patients with renal events and percentage will be provided for clinical signs and symptoms by the treatment. The criteria for renal events are displayed in [Table 2-8](#).

Renal event overview data, pathology data, and imaging data will be provided in listings.

The renal function lab data will be analyzed in [Section 2.8.3](#) Laboratory data.

Table 2-8 Specific renal alert criteria

Criteria	Action required
Serum event	
Serum creatinine increase 25 – 49 % compared to BL	Confirm 25 % increase after 24-48h Follow up within 2-5 days
Acute kidney injury: serum creatinine increase ≥50 % compared to BL	Follow up within 24-48h if possible Consider study treatment interruption Consider subject hospitalization /specialized treatment
Urine event	
New dipstick proteinuria ≥ 1+	Confirm value after 24 to 48h
Albumin- or protein-creatinine ratio increase ≥2-fold	Perform urine microscopy Consider study treatment interruption / or discontinuation
Albumin-creatinine ratio (ACR) ≥30 mg/g or ≥3 mg/mmol; Protein-creatinine ratio (PCR)≥150 mg/g or >15 mg/mmol	
New dipstick hematuria ≥ 1+ not due to trauma	Urine sediment microscopy Perform serum creatinine, ACR

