4.1 Inclusion criteria

Patients/subjects eligible for inclusion in this study must fulfill all of the following criteria:

1. Written informed consent must be obtained before any assessment is performed.
 2. Male and female, age 20 to 75 years old, both inclusive at Visit 1
 3. Patients with obesity disease and inadequately controlled body weight with diet and/or exercise for three months prior to Visit 1
 - BMI ≥ 25 kg/m² combined with at least two obesity-related comorbidities* at Visit 1 and 201
 - BMI ≥ 35 kg/m² at least one obesity-related comorbidity at Visit 1 and 201
- *Obesity-related comorbidities are ([Japan Society for the Study of Obesity 2016](#));
- Glucose tolerance impaired (T2DM, impaired glucose tolerance etc.)
 - Dyslipidemia
- 

- Hypertension
 - Hyperuricemia and gout
 - Coronary artery disease: myocardial infarction and angina pectoris
 - Cerebral infarction: cerebral thrombosis and transient ischemic attack
 - Nonalcoholic fatty liver disease
 - Abnormality in menstruation and infertility
 - Obstructive sleep apnea syndrome and obesity-hypoventilation syndrome
 - Locomotive diseases: Osteoarthritis (knee, hip) and Spinal osteoarthritis, Finger osteoarthritis
 - Obesity related glomerulopathy
4. Patients with FPG \geq 110 mg/dL and/or $5.6\% \leq$ HbA1c \leq 10.0%, or T2DM with HbA1c \leq 10.0% at Visit 1
 5. Waist circumference at umbilical level \geq 85 cm for male, \geq 90 cm for female at Visit 1
 6. Visceral fat area \geq 100 cm² at Visit 102.
 7. Agreement to comply with the study-required life-style intervention and treatment during the full duration of the study

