7.4 Renal safety monitoring

The following two categories of abnormal renal laboratory values have to be considered during the course of the study:

- Serum event:
 - confirmed (after ≥ 24 h) increase in serum creatinine of $\geq 25\%$ compared to baseline during normal hydration status
- Urine event
 - new onset ($\geq 1+$) proteinuria; confirmed by doubling in the urinary albumin-creatinine ratio (ACR) or urinary protein-creatinine ratio (PCR) (if applicable)
 - new onset ($\geq 1+$), hematuria or glycosuria

Every renal laboratory trigger or renal event as defined in [Table 15-1 in Appendix 3](#) should be followed up by the investigator or designated personnel at the trial site as summarized in [Appendix 3](#).

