> 1.5 to ≤ 2 × ULN (patient is asymptomatic)	
 Repeat LFT within the next week If elevation is confirmed, initiate close observation of the patient 	Investigator discretion Monitor LFT within 1 to 4 weeks or at next visit
Jaundice	
 Discontinue the study treatment immediately Hospitalize the patient Establish causality Complete liver CRF 	ALT, AST, TBL, Alb, PT/INR, ALP and γGT until resolution ^c (frequency at investigator discretion)
Any AE potentially indicative of a liver toxicity*	
 Consider study treatment interruption or discontinuation Hospitalization if clinically appropriate Establish causality Complete liver CRF 	Investigator discretion

^aElevated ALT/AST > 3 × ULN and TBL > 2 × ULN but without notable increase in ALP to > 2 × ULN

^b(General) malaise, fatigue, abdominal pain, nausea, or vomiting, or rash with eosinophilia

^cResolution is defined as an outcome of one of the following: (1) return to baseline values, (2) stable values at three subsequent monitoring visits at least 2 weeks apart, (3) remain at elevated level after a maximum of 6 months, (4) liver transplantation, and (5) death.

15 Appendix 3: Specific Renal Alert Criteria and Actions

Table 15-1 Specific Renal Alert Criteria and Actions

Serum Event	
Serum creatinine increase 25 - 49% compared to baseline	Confirm 25% increase after 24-48h Follow up within 2-5 days
Acute Kidney Injury: Serum creatinine increase ≥ 50% compared to baseline	Follow up within 24-48h if possible Consider study treatment interruption Consider patient hospitalization /specialized treatment
Urine Event	
New dipstick proteinuria ≥ 1+ Albumin- or Protein-creatinine ratio increase ≥ 2-fold Albumin-creatinine ratio (ACR) ≥ 30 mg/g or ≥ 3 mg/mmol; Protein-creatinine ratio (PCR) ≥ 150 mg/g or > 15 mg/mmol	Confirm value after 24-48h Perform urine microscopy Consider study treatment interruption / or discontinuation
New dipstick glycosuria ≥ 1+ not due to diabetes	Blood glucose (fasting) Perform serum creatinine, ACR
New dipstick hematuria ≥ 1+ not due to trauma	Urine sediment microscopy Perform serum creatinine, ACR
For all renal events:	

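### The ACR/PCR threshold in the SAP's renal event criteria has no baseline condition and is not reconciled with Protocol Section 7.4

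*SAP*

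**What the plan says.** SAP 2.8.6 states: "The criteria for renal events are displayed in" Table 2-8. Patients with renal events during Epoch 3 "will be provided by treatment and the first identified criterion". The lines of Table 2-8 are:

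- two serum creatinine rises, both relative to baseline;
- new dipstick proteinuria of at least 1+;
- an ACR or PCR increase of at least 2-fold;
- "Albumin-creatinine ratio (ACR) ≥30 mg/g or ≥3 mg/mmol; Protein-creatinine ratio (PCR)≥150 mg/g or >15 mg/mmol";
- new dipstick hematuria not due to trauma.

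The threshold line comes from Protocol Appendix 3, Table 15-1: "Albumin-creatinine ratio (ACR) ≥ 30 mg/g or ≥ 3 mg/mmol", followed by the same PCR limits and likewise with no baseline reference.

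Protocol Section 7.4 describes the urine event differently, as new-onset "proteinuria; confirmed by doubling in the urinary albumin-creatinine ratio (ACR) or urinary protein-creatinine ratio (PCR) (if applicable". The same section then requires follow-up of "Every renal laboratory trigger or renal event as defined in" Table 15-1, so it also relies on the appendix.

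Patients can enter with albuminuria. Section 4.1 lists "Obesity related glomerulopathy" among the qualifying comorbidities, Section 5.3 aims for at least 45% of patients in each glycemic stratum, and Section 4.2 has no exclusion for albuminuria. Table 6-1 schedules ACR at Visits 201 and 299 only.

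**The concern.** An absolute threshold with no baseline condition measures who has albuminuria, not who developed it. Roughly half of this population has type 2 diabetes, so some patients may be above 30 mg/g before the first dose. Counting them as having Epoch 3 events would add cases unrelated to treatment to every arm and pull the ratio between arms towards 1. Randomization balances these carried-over cases only in expectation. If LIK066 lowers ACR, fewer would remain in the active arms, which could offset truly new events there.

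A second problem lies inside the protocol. Section 7.4 and Table 15-1 give sites two descriptions of the urine event, and the actions in Table 15-1 attach to the broader one.

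**Working it through.** No sample size, power or expected event count in the documents depends on this point, so there is no stated figure to reproduce. The check is a comparison of texts, followed by an illustration.

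**1. Qualifiers, line by line (SAP Table 2-8)**

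| Line | Condition tying it to change |
|---|---|
| Creatinine +25–49% | compared to baseline |
| Creatinine +50% or more | compared to baseline |
| Dipstick proteinuria | new |
| ACR or PCR 2-fold | increase |
| ACR ≥30 mg/g, PCR ≥150 mg/g | none |
| Dipstick hematuria | new |

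Appendix 3 also defines resolution relative to baseline, with PCR within 50% of it. A PCR unchanged from a baseline of 150 mg/g or more would meet the threshold line and the resolution rule at once.

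**2. Two readings.** Take an ACR of 200 mg/g at Visit 201 and 100 mg/g at Visit 299.

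- Alternatives: 100 ≥ 30, so the patient counts.
- Joint conditions: 100/200 = 0.5, which is below 2, so the patient does not count.

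**3. Simple size.** Assume 10–25% of patients have ACR ≥30 mg/g at baseline.

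- All patients: 0.10 × 130 = 13; 0.25 × 130 = 32.5, about 33.
- Arm of 20: 2 to 5. Arm of 30: 3 to 7.5, about 8.

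These are upper limits for carried-over cases, because some patients will be below 30 mg/g at Week 12.

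**4. Effect on a comparison.** Assume 1/30 new events on placebo, 3/30 at 50 mg, and 5 carried-over cases in each arm.

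- Ratio: 3/1 = 3.0 becomes (3+5)/(1+5) = 8/6 = 1.33.
- Difference: 3/30 − 1/30 = 2/30, and 8/30 − 6/30 = 2/30, so it is unchanged.

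**5. Illustrative simulation.** There were 1,000,000 subjects per scenario, scaled to 130. Every input is an assumption. Log ACR is u + e₁ at baseline and u + ln(r) + e₂ at Week 12. The SD of u is 1.1, and the variance of each e is ln(1 + CV²) with within-subject CV 30% or 50%. The Week 12 to baseline ratio r is 1.0 or 0.7, and the mean is set to give baseline prevalence p. Ranges run over CV and r.

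| p | ≥30 at Week 12 (of 130) | of these, ≥30 at baseline | of these, below own baseline | ≥30 and doubled (of 130) | newly ≥30 (of 130) |
|---|---|---|---|---|---|
| 10% | 7.2–13.0 | 61–90% | 31–69% | 0.1–3.7 | 0.8–5.1 |
| 20% | 16.1–26.0 | 69–92% | 34–71% | 0.2–6.5 | 1.3–8.2 |
| 30% | 26.1–39.0 | 74–94% | 37–73% | 0.3–9.0 | 1.7–10.1 |

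The last column is the simulated proportion times 130, for example 0.063 × 130 = 8.2. A joint reading would also need a new positive dipstick, so the doubled column is an upper limit for it. Under these assumptions the count changes severalfold with the reading chosen.

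**The case against.** A reader might infer that existing albuminuria is certain to be counted, even when it improves. The documents do not support that. In Table 15-1 the dipstick, 2-fold and threshold lines run together against one action block, which fits a joint criterion in the spirit of Section 7.4. The cell layout cannot be recovered from the extracted text. Tabulation by first identified criterion favors alternatives but does not settle it.

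The data source is also open. The liver section (SAP 2.8.5) counts subjects who meet criteria after baseline. The renal section has no such wording and lists renal event overview data, so its counts may come from site-reported events rather than from every Week 12 ACR. This objection stands.

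A reader might also infer that a dose-related renal signal would be hidden. That goes too far. The creatinine criteria are relative to baseline. SAP 2.8.3 plans shift tables where ranges exist, SAP 2.7.2 analyzes the change in UACR with baseline as a covariate, and impaired renal function is a separate adverse event grouping. Exclusion of eGFR below 60 limits established renal disease, though not albuminuria.

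Two more inferences fail. Because Section 7.4 itself points to Table 15-1, one cannot say flatly that it would not call an unchanged ACR an event. And a raised Week 12 ACR beside a lower mean UACR is two different summaries, not a contradiction.

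None of this supplies the missing connector, data source or baseline condition.

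**Conclusion.** The point holds in a limited form. The threshold line is the only one in Table 2-8 with no condition on change. Its relation to Section 7.4 is unstated, and on the more natural reading it would count unchanged or improving albuminuria as an Epoch 3 renal event. That is more than missing detail, because the stated criterion conflicts with the protocol's own description of the urine event.

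The size is unknown: at most 13–33 of 130 patients if baseline prevalence is 10–25%, which is an assumption. The consequence is a diluted ratio in one descriptive safety table, and it arises only if the line stands alone and is applied to laboratory values. The primary analysis, type I error and power are untouched, as are the other renal displays.

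**What to change.** In SAP 2.8.6 and Table 2-8, before unblinding:

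1. State whether the dipstick, 2-fold and threshold lines are alternatives or joint conditions.
2. State whether counts come from the CRF or from laboratory data.
3. Count the ACR/PCR threshold as an Epoch 3 event only if the baseline value was below it or the ratio at least doubled from baseline.
4. Show patients already above the threshold at baseline in a separate row, and say how a missing baseline value is handled.

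This follows the SAP's own practice for vital signs (2.8.4.2), which counts newly occurring or worsening values. For site action, the sponsor must reconcile Section 7.4 with Table 15-1; no clinical rule is proposed here.

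The cost is SAP wording, a clarifying line in the protocol and slightly more programming. Baseline ACR is already collected at Visit 201. Fewer events will be counted. Chance crossings of the threshold will remain: with no true change (r = 1.0), the simulation gives 0.025–0.078 × 130, about 3–10 patients newly at or above 30 mg/g. Those crossings are not tied to treatment, and the separate row keeps the excluded patients visible.
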